#### 9.1.6. Open label extension phase (Day 56±7- day 112±7)

- According to their visit 4 HDRS response assessment, subjects will be assigned into one of three open label treatment groups: Remitters/Responders/Non responders as follows:
  - Remitters: HDRS ≤7 at study visit 4 (week 8±1 post treatment initiation).
  - Responders: 50% ≥ HDRS score improvement from baseline at study visit 4 (week 8±1 post treatment initiation).
  - Non-responders: all other subjects who are not remitters or responders (50% <HDRS score improvement from baseline) at study visit 4 (week 8±1 post treatment initiation).

See Figure 5: Open label phase study flow.

 Neurolief Brain Innovation	MOOD: CLINICAL INVESTIGATION PLAN	Doc No.: CL-CIP-201 Rev: REV.3 / 09June2021 Pg. 50 of 92
--	--	--

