8.2 Secondary Efficacy Endpoints

Secondary efficacy endpoints include:

- **Proportion of responder subjects** - defined as the percent of subjects achieving at least 50% reduction from baseline in their HDRS-17 total score, 8 weeks post Relivion®DP treatment initiation.

- **Proportion of subjects achieving remission** - defined as the percent of subjects with HDRS-17 score≤7 at 8 weeks post Relivion®DP treatment initiation.
- **Change from baseline** to week-8 post Relivion®DP treatment initiation **in depressive symptoms** as measured by **MADRS** total score.

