11.5.2 Subset Analyses

The primary endpoint will be presented descriptively for the following subsets in addition they will be entered as additional covariates in the primary efficacy endpoint ANCOVA model to evaluate their effect on the change from baseline HDRS-17 score:

- Age Group (by median age)
- Sex (at birth)
- Baseline HDRS-17 severity (≥ 26 , 20-25, 17-19)
- Baseline Resistance, ATRF 1 vs. 2-4
- Concomitant anti-anxiety medication use, Yes/No
- Concomitant insomnia (includes anti-anxiety medications used to treat insomnia at bedtime) medication use, Yes/No
- Concomitant anticonvulsant medication use, Yes/No
- Comorbidities migraine and pain disorders, Yes/No
- Past history of ECT, TMS or VNS treatment, Yes/No
- Subjects on subtherapeutic dose of antidepressant, Yes/No
- Blinding assessment - The effect of potential unblinding will be evaluated as a sensitivity analysis, where an additional binary variable identifying subjects correctly guessed their treatment assignment versus those who did not will be added to the ANCOVA model as a covariate.

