11.5.7 Additional Exploratory Endpoints and Analyses - Open Label Stage

1. The following endpoints will only be evaluated in the Relivion®DP treatment group for the mITT analysis set:

- Change from Baseline to 16 weeks post Relivion®DP treatment initiation in HDRS-17 (Visit 6).

The change from baseline HDRS-17 score will be modeled with a repeated measures ANCOVA model. The change will be modeled as a function of visit (categorical) with baseline value entered as a covariate. LSmean changes in HDRS-17 scores will be estimated from the model per visit and for the difference between visits and will be presented with 95% confidence intervals as well as level of significance (testing the null hypothesis

LSmean=0). The change from baseline in HDRS-17 score at visit 6 will also be compared to the change at visit 4.

- **Proportion of HDRS-17 responder subjects to visit 6.** The percent of subjects achieving at least 50% reduction from baseline in HDRS-17 total score to each visit in the original active group will be summarized by a count and percentage and compared between the visits using a GEE model (repeated measures model for binary data) programmed in the SAS GENMOD Procedure which will account for the within subject correlation, baseline HDRS-17 score will be entered as a covariate.

- **Proportion of subjects achieving clinically substantial improvement in HDRS-17 scores to visit 6,** defined as the percent of subjects with reduction in HDRS-17 score of at least 7 points at 16 weeks post Relivion®DP treatment initiation.

The percent of subjects achieving clinically substantial improvement in HDRS-17 scores at each visit in the original active group will be summarized by a count and percentage and compared between the visits using a GEE model (repeated measures model for binary data) programmed in the SAS GENMOD Procedure which will account for the within subject correlation, baseline HDRS-17 score will be entered as a covariate.

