- **Proportion of subjects achieving remission at visit 6** - defined as the percent of subjects with HDRS17 score≤7 at 16 weeks post Relivion®DP treatment initiation in the original active group. The percent of subjects achieving remission at each visit in the original active group will be summarized by a count and percentage and compared between the visits using a GEE model (repeated measures model for binary data) programmed in the SAS GENMOD Procedure which will account for the within subject correlation, baseline HDRS-17 score will be entered as a covariate.
- **HDRS-17 Category Shift from Visit 2 to Visit 6** – defined as the category change from baseline to week-16 post Relivion®DP treatment initiation in HDRS-17; Categories definition: 5: Very severe 26-52, 4: Severe 20-25, 3:

Moderate 14-19, 2: Mild 13-8 and 1: 0-7 Remission. The category shift will be tabulated and summarized by a count and percent.

- **Proportion of new responder subjects** - defined as the percent of subjects who did not have a remission (per HDRS-17) at visit 4, achieving at least 50% reduction from baseline (Visit 2) in HDRS-17 total score 16 weeks post Relivion®DP active treatment initiation (Visit 6). A count and percentage with two-sided exact 95% confidence interval will be presented.
- **Proportion of new subjects achieving remission** - defined as the percent of subjects who did not have a remission (per HDRS-17) at visit 4, achieving a HDRS-17 total score \leq 7 points 16 weeks post Relivion®DP active treatment initiation (Visit 6). A count and percentage with two-sided exact 95% confidence interval will be presented.
- **Change from baseline to 16 weeks (Visit 6) post Relivion®DP treatment initiation in the Clinical Global Impression Severity scale (CGI-S) score.** The change from baseline CGI-S score will be modeled with a repeated measures ANCOVA model. The change will be modeled as a function of visit (categorical) with baseline value entered as a covariate. LSmean CGI-S changes from baseline will be estimated from the model per visit and for the difference between visits and will be presented with 95% confidence intervals as well as level of significance (testing the null hypothesis LSmean=0). The change at visit 6 will also be compared to the change at visit 4.

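### SAP 11.5.7 counts new responders among Visit 4 non-remitters, so subjects who had already responded at Visit 4 can be counted as new

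*SAP*

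**What the plan says.** SAP 11.5.7 lists open-label endpoints that are introduced this way: "The following endpoints will only be evaluated in the Relivion®DP treatment group for the mITT analysis set". One is the proportion of new responders, defined as subjects "who did not have a remission (per HDRS-17) at visit 4, achieving at least 50% reduction from baseline" (Visit 2) at Visit 6. The bullet after it, on new remissions, uses the same Visit 4 condition: "who did not have a remission (per HDRS-17) at visit 4, achieving a HDRS-17 total score" of 7 or less at Visit 6. Both are reported as a number and percentage with an exact 95% confidence interval.

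SAP 8.2 keeps the two states apart. The responder proportion is "defined as the percent of subjects achieving at least 50% reduction from baseline in their HDRS-17 total score" at week 8, and the remission proportion is "defined as the percent of subjects with HDRS-17 score≤7 at 8 weeks post Relivion®DP treatment initiation". Protocol 9.1.6 also separates them at Visit 4: "subjects will be assigned into one of three open label treatment groups: Remitters/Responders/Non responders as follows". A subject who responds without remitting is therefore a recognised category, distinct from a non-responder.

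Neither document limits new responders to subjects who were non-responders at Visit 4.

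**The concern.** A subject can be new to response at Visit 6 only if not in response at Visit 4. The definition excludes Visit 4 remitters but keeps Visit 4 responders who did not remit. If they still show a 50% reduction at Visit 6, they enter the numerator although nothing was gained after Visit 4. If they lose response, they stay in the denominator as failures to convert, although they were never candidates for conversion.

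At stake is how the percentage will be read. A new-responder figure in a pivotal trial report invites the reading that this share of subjects first responded during the second eight weeks. As defined, it mixes conversion with response carried over from the double-blind phase.

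**Working it through.** The documents state no figure for this endpoint, so there is none to reproduce. The check has three steps.

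**1. Can a subject respond without remitting at this trial's baselines?** Response means a score of at most half of baseline; remission means a score of 7 or less. The lowest baseline stratum in SAP 11.5.2 starts at 17: "Baseline HDRS-17 severity (≥ 26 , 20-25, 17-19". The Visit 4 scores that are response without remission are:

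| Baseline HDRS-17 | Response without remission | Remission without response |
|---|---|---|
| 14, 15 | none | none |
| 16, 17 | 8 | none |
| 20 | 8–10 | none |
| 26 | 8–13 | none |
| 30 | 8–15 | none |

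At baselines of 17 and above, the Visit 4 non-remitters are thus the non-responders plus the responders who did not remit. Example: baseline 24 and score 12 at both visits. The reduction is 12/24 = 50% (response), and 12 is above 7 (no remission). SAP 11.5.7 counts this subject as a new responder.

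**2. How large is the overlap?** The share of Visit 4 non-remitters who already respond is (response − remission) / (1 − remission).

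- Feasibility study of this device (Protocol 7.6.2), response and remission both 8/23: (8 − 8) / (23 − 8) = 0%.
- Assumed rates of 35% response and 20% remission: (0.35 − 0.20) / (1 − 0.20) = 0.15/0.80 = 18.75%, about 19%.

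**3. What does this do to the reported percentage?** Let Q be the Visit 4 responders who did not remit, N the Visit 4 non-responders, m the share of Q still in response at Visit 6, and c the share of N who convert.

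- As written: (mQ + cN) / (Q + N)
- With non-responders as the denominator: c
- Difference: [Q / (Q + N)] × (m − c)

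The SAP wording overstates conversion when m exceeds c, and understates it when m is below c.

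In the illustration, 53 active subjects is the planned evaluable number per arm in Protocol 12.4. All else is assumed: 11 Visit 4 remitters, hence 42 non-remitters, about 80% retention, and either no conversion or about 20%, with counts rounded to whole subjects.

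| Q | As written, no conversion | Corrected | As written, about 20% conversion | Corrected |
|---|---|---|---|---|
| 0 | 0/42 = 0% | 0/42 = 0% | 8/42 = 19.0% | 8/42 = 19.0% |
| 5 | 4/42 = 9.5% | 0/37 = 0% | 11/42 = 26.2% | 7/37 = 18.9% |
| 8 | 6/42 = 14.3% | 0/34 = 0% | 13/42 = 31.0% | 7/34 = 20.6% |
| 12 | 10/42 = 23.8% | 0/30 = 0% | 16/42 = 38.1% | 6/30 = 20.0% |

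For Q = 8 the exact 95% intervals are 5.4–28.5% against 0–10.3% with no conversion, and 17.6–47.1% against 8.7–37.9% with about 20% conversion.

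The reverse case is possible. If only 1 of the 8 keeps response and 7 of 34 convert, the SAP wording gives (1 + 7)/42 = 19.0%, below the corrected 7/34 = 20.6%.

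**The case against.** The strongest reply is that little depends on this line. It is exploratory, confined to the original active arm, has no comparator or test, and lies outside the testing hierarchy of SAP 9.2. SAP 11.5.7 also reports the HDRS-17 responder proportion at each visit in the same arm and compares visits with a GEE model. The subject with 12 at both visits is a responder at both and adds no gain there. This stands and limits the consequence. The GEE comparison gives net change, however, with conversions and losses offset, so it does not supply the individual conversions that a new-responder count promises.

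A second reply is that non-remitters may have been chosen on purpose. Item 3 of SAP 11.5.7 uses them as a population too, and response at Visit 6 among Visit 4 non-remitters is a coherent quantity. That also stands, but item 3 measures score change and claims no newness. If this is the intention, the name is what is wrong. A reader might infer from the identical condition in the new-remission bullet that the phrase was copied by mistake; the documents do not show how it arose.

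A third reply is that the overlap may be empty. The feasibility data are consistent with that, although they come from 23 subjects at six weeks. This bears on the size, not on whether the rule is right.

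**Conclusion.** The definition is wrong as written: followed exactly, it counts some Visit 4 responders as new responders at Visit 6, and nothing elsewhere in the documents corrects it. The consequence is confined to one descriptive percentage.

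Three stronger readings are tempting and are not supported:

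- That a known, substantial share of the reported new responders will be spurious. The documents give no Visit 4 rates for this trial. The overlap is 0% at the feasibility rates. The figure of about 19% rests on assumed rates, and it becomes the reported percentage without any conversion only if every such subject keeps the response.
- That correcting the definition must lower the percentage. It does so only if retention among Visit 4 responders who did not remit exceeds conversion among non-responders. That is the likelier case, but not a certain one. If there are no such responders, the two definitions agree.
- That the trial's efficacy conclusions are inflated. The primary and secondary endpoints are week 8 comparisons between arms and do not use this definition.

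**What to change.** In SAP 11.5.7, define new responders as subjects in the original active group with less than 50% HDRS-17 reduction from baseline at Visit 4 who reach at least 50% at Visit 6, with Visit 4 non-responders as the denominator. Keep the count, percentage and exact interval.

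If non-remitters are the intended population, leave the calculation alone and rename the endpoint response at Visit 6 among Visit 4 non-remitters.

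Either change is one sentence and uses HDRS-17 scores already collected at Visits 2, 4 and 6. The first reduces the denominator and so widens the interval somewhat. If the analysis has already been run, describe and justify the change in the clinical study report, as SAP 11.1 provides for deviations from the planned analysis.

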#### 12.2.2. Secondary and exploratory endpoint variables

The secondary endpoints of responder and remission will be represented in the form of binary variables which will be assigned the value of "1" if the subject is a "responder" or a "remitter" per specific secondary endpoint, and "0" otherwise. Other exploratory binary endpoints will be defined in a similar manner.

Secondary and exploratory endpoints described as changes from baseline, such as QIDS-SR-16, CGI-S and CGI-I and MDRS will be calculated by subtracting the subject's baseline score from the score at each visit.

 Neurolief Brain Innovation	MOOD: CLINICAL INVESTIGATION PLAN	Doc No.: CL-CIP-201 Rev: REV.3 / 09June2021 Pg. 70 of 92
--	--	--

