1. INTRODUCTION

This Statistical Analysis Plan (SAP) is a more detailed companion to the Statistical Methods section of the study titled “The MOOD study – external Combined Occipital and Trigeminal Nerve Stimulation (eCOT-NS) for the treatment of Major Depressive Disorder (MDD)” and provides a comprehensive description of the analysis sets, endpoints, methods, and data analyses to be used. This SAP prevails when differences exist in descriptions or explanations provided in the protocol and the SAP. We shall address analysis strategies for the open label stage of the study. Addressed as well is a plan for prognostic factor analysis to identify potential baseline parameters related to the primary endpoint and its derivatives.

Relivion®DP, an external Combined Occipital and Trigeminal Afferent Stimulation (eCOT-AS) is proposed as a novel treatment for MDD. The combination of neuromodulation of both the occipital and the trigeminal nerve branches non-invasively is made possible for the first time, after having been successfully performed either separately or in invasive procedures.

Major depressive disorder is one of the leading causes of disability worldwide. However, treatment options are still limited, therefore new approaches are needed to enhance clinical improvement. The non-invasive combined neuromodulation of both the occipital and trigeminal nerve branches is a safe, self-administered novel technology with high potential for treating MDD patients. Based on this rationale, Neurorelief developed the Relivion®DP, a neuro-stimulator applying combined occipital and trigeminal afferent stimulation for treatment of major depressive disorder (MDD). Following completion of an early clinical study showing promising results, Neurorelief designed the proposed clinical trial to evaluate the safety and efficacy of the Relivion®DP in a two-arms controlled, double blinded randomized study.

The MOOD Study will evaluate the safety and efficacy of a self-administered treatment for MDD using an external combined occipital and trigeminal afferent stimulator (Relivion®DP).

This pivotal clinical investigation is intended to support future marketing applications (US FDA and CE) for Neurorelief’s Relivion®DP device.

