11.5.5 Tertiary Endpoints Analyses

- Mean Change in the CGI-S score - at 8 weeks post treatment initiation– will be compared between the groups using a similar model as the primary endpoint.
- Mean CGI-I scores at 8 weeks post treatment initiation will be compared between the groups using a similar model as the primary endpoint but with the value at each visit modeled instead of the change.
- Mean change from baseline in total score of the Quick Inventory of Depressive Symptomatology self-rated (QIDS-SR-16) score at 8 weeks post treatment initiation– will be compared between the groups using a similar model as the primary endpoint.
- Mean change in depressive symptoms, measured by HDRS-21 total score, from baseline to week 8 post Relivion®DP treatment initiation will be compared between the groups using a similar model as the primary endpoint.
- Proportion of subjects with a clinically substantial reduction in HDRS-17 score defined as the percent of subjects with reduction in HDRS-17 score of at least 7 points at 8 weeks post Relivion®DP treatment initiation - will be summarized by a count and percentage and compared between the groups with a chi-squared test and a Fisher's exact test. The odds ratio with 95% Wald confidence interval will be presented as well. As an additional measure of effect size the NNT will be presented.
- HDRS-17 total score at visit 4 (week-8 post Relivion®DP treatment initiation) will be compared between the groups using a similar model as the primary endpoint using the HDRS-17 score at each visit instead of the change.
- HDRS-17 Category Shift from Visit 2 to Visit 4 – defined as the category change from baseline to week-8 post Relivion®DP treatment initiation in HDRS-17; Categories definition: 5: Very severe 26-52, 4: Severe 20-25, 3: Moderate 14-19, 2: Mild 13-8 and 1: 0-7 Remission, will be summarized by a count and

percentage and compared between the groups with a Cochran-Armitage trend test.

- Mean change in Q-LES-Q score at visit 4 – measured as the difference between the baseline and visit 4 Q-LES-Q percentage of maximum total scores, will be compared between the groups using analysis of variance (ANOVA).

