- **Clinical Global Impression Improvement (CGI-I) score over time to Visit 6.** The CGI-I score (from visit 3) will be modeled with a repeated measures ANCOVA model. The score will be modeled as a function of visit (categorical). LSmean CGI-I scores will be estimated from the model per visit and for the difference between visits and will be presented with 95% confidence intervals as well as level of significance (testing the null hypothesis LSmean=0). The CGI-I score at visit 6 will be compared to the score at visit 4.

- **Change from baseline to week-16 (visit 6) post Relivion®DP treatment initiation in the total score of the Quick Inventory of Depressive Symptomatology (self-rated) (QIDS-SR-16).** The change from baseline QIDS-SR-16 score will be modeled with a repeated measures ANCOVA model. The change will be modeled as a function of visit (categorical) with baseline value entered as a covariate. LSmean QIDS-SR-16 changes from baseline will be estimated from the model per visit and for the difference between visits and will be presented with 95% confidence intervals as well as level of significance (testing the null hypothesis LSmean=0). The change at visit 6 will also be compared to the change at visit 4.
- **Change from baseline Q-LES-Q score at Visit 6** – measured as the difference between the baseline and visit 6 Q-LES-Q percentage of maximum total scores. The change from baseline Q-LES-Q score will be modeled with a repeated measures ANCOVA model. The change will be modeled as a function of visit (categorical) with baseline value entered as a covariate. LSmean Q-LES-Q changes from baseline will be estimated from the model per visit and for the difference between visits and will be presented with 95% confidence intervals as well as level of significance (testing the null hypothesis LSmean=0). The change at visit 6 will also be compared to the change at visit 4.

2. The following endpoints will be analyzed on all subjects that completed visit 6 grouped together regardless of prior double-blind treatment:

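### The open-label CGI-I score is modelled as a raw value, but its per-visit LS means are tested against zero, a null that fits only change scores

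*SAP*

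**What the plan says.** SAP 11.5.7 lists open-label endpoints that "will only be evaluated in the Relivion®DP treatment group for the mITT analysis set". For CGI-I the outcome is the score, starting at Visit 3: "The score will be modeled as a function of visit (categorical"). No baseline is subtracted and no baseline covariate is entered. Two kinds of quantity are then estimated: "LSmean CGI-I scores will be estimated from the model per visit and for the difference between visits". Both get 95% confidence intervals and a significance level, with the null stated as follows: "testing the null hypothesis LSmean=0). The CGI-I score at visit 6 will be compared to the score at visit 4".

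The HDRS-17, CGI-S, QIDS-SR-16 and Q-LES-Q items in the same section carry the same null, but their outcome is a change from baseline. For CGI-S, for example: "The change from baseline CGI-S score will be modeled with a repeated measures ANCOVA model".

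The SAP draws this distinction in 11.5.5, where the double-blind CGI-I comparison is to be run "with the value at each visit modeled instead of the change".

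Protocol 12.2.2 differs: "Secondary and exploratory endpoints described as changes from baseline, such as QIDS-SR-16, CGI-S and CGI-I and MDRS will be calculated by subtracting" the baseline score from the score at each visit. SAP section 1 settles which text governs: "This SAP prevails when differences exist in descriptions or explanations provided in the protocol and the SAP".

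**The concern.** A test of LS mean = 0 answers a useful question when the outcome is a change, because zero then means that nothing moved. CGI-I is the only repeated-measures item in SAP 11.5.7 that models a score instead of a change, and its null was not adapted. If the lowest possible score is above zero, the null cannot be true. The per-visit p-value then only confirms that the scale does not reach zero.

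What is at stake is how the results read. A very small CGI-I p-value would appear at every visit, in the same format as the genuine change-from-baseline p-values beside it. It could be taken as evidence of improvement in a study meant to support US and European marketing applications.

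**Working it through.** **Inputs**

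- n = 53 evaluable per arm, two-sided 5% (Protocol 12.4).
- The CGI-I coding, its no-change point and its SD are not given. Assumed: scores 1-7 with 4 = no change, SD 0.5 to 2. Scales 1-5 and 1-10 were also tried.
- The LS mean at a visit is approximated by the sample mean at that visit, tested with a one-sample t.

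**The plan's own n.** A difference of 3.3 with SD 6 is an effect size of 3.3/6 = 0.55. The exact two-sample t-test at 80% power needs 52.87 per arm, rounded up to 53, where power is 80.1%. The stated 53 reproduces.

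**Step 1: the test as written.** t = mean / (SD/√n), with √53 = 7.28 and critical value 2.007.

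| True state | SD | t against 0 |
|---|---|---|
| No change, mean 4 | 0.5 | 4 × 7.28 / 0.5 = 58.2 |
| No change, mean 4 | 1 | 29.1 |
| No change, mean 4 | 1.5 | 19.4 |
| No change, mean 4 | 2 | 14.6 |
| Worsened, mean 5 | 1 | 5 × 7.28 / 1 = 36.4 |

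**Step 2: the smallest t that any data can give.** On a scale from 1 to b, the ratio of SD (divisor n) to mean cannot exceed (b − 1)/(2√b). Hence t ≥ √(n − 1) / [(b − 1)/(2√b)]. With n = 53, √52 = 7.211:

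- 1-7: ratio 6/(2√7) = 1.134; minimum t = 6.36. A search over all mixtures of the two extreme scores also gave 6.36.
- 1-5: ratio 4/(2√5) = 0.894; minimum t = 8.06.
- 1-10: ratio 9/(2√10) = 1.423; minimum t = 5.07.

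The number reaching the open-label visits may be below 53. On 1-7 the minimum is 5.72 at n = 43, 4.75 at n = 30 and 3.84 at n = 20. Rejection is certain from n = 9.

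**Step 3: simulation.** 20,000 replicates, n = 53, integer scores 1-7, latent SD 1.2, within-subject correlation 0.5. The table shows rejection rates.

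| Mean at Visit 4, Visit 6 | Visit 6 mean against 0 | Visit 6 mean against 4 | Visit 6 − Visit 4 against 0 |
|---|---|---|---|
| 4, 4 (no change) | 100% | 5.1% | 5.3% |
| 5, 5 (worse) | 100% | 100% | 5.3% |
| 2.5, 2.5 (improved, flat) | 100% | 100% | 4.9% |
| 3, 2.5 (improving) | 100% | 100% | 79% |

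The test against 0 cannot tell the four states apart. Against the assumed no-change value, the test holds its 5% level when nobody changes, and the sign of the difference shows the direction. The between-visit contrast behaves properly with its null at zero.

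**The case against.** Four points on the other side have force.

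**The zero null is right for part of what it covers.** The same parenthesis applies to the differences between visits, and the Visit 6 versus Visit 4 comparison follows it. A reader might infer that the whole open-label CGI-I analysis is uninformative. The documents do not support that, because zero is the correct null for a difference and the simulation agrees.

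**The 11.5.5 wording could be read as a second instance.** It is not. There the CGI-I value is compared between active and sham, so the tested quantity is a difference between arms. The section shows only that the SAP treats CGI-I as a value.

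**Protocol 12.2.2 lists CGI-I among variables computed as score minus baseline,** and Protocol 9.1.2 collects CGI-I at Visit 2. With that subtraction, zero would be a meaningful null. But the SAP says that it prevails, and it models the score from Visit 3 without subtraction, so this does not rescue the per-visit test.

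**The coding is not in the documents.** A coding centred on zero would remove the problem, but neither document describes one. The objection stands as a condition on the finding.

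The per-visit means and confidence intervals are also already planned, so a careful reader could judge the ratings without the p-value. That limits the harm but gives the p-value no purpose.

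**Conclusion.** The point holds for the per-visit CGI-I tests in SAP 11.5.7 and for nothing wider. If the lowest CGI-I score is above zero, those tests reject under improvement, no change and worsening alike. The conclusion does not depend on the exact range: on all three scales tried, the minimum possible t at n = 53 is more than twice the critical value. The figures for a group with no change do depend on the assumed 1-7 coding with 4 as no change, and on the SD range.

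A reader might take this as a threat to the trial's conclusions. It is not. The endpoint is exploratory, open-label and limited to the original active arm. It also lies outside the testing hierarchy in SAP 9.2, which covers primary, secondary and tertiary endpoints. The primary result and type I error control do not change. This is a minor correction.

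**What to change.** In the CGI-I item of SAP 11.5.7, do one of the following:

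- delete the significance level for the per-visit LS means, and keep each LS mean with its 95% CI; or
- state the CGI-I coding and test each per-visit LS mean against its no-change value.

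In either case, keep the between-visit differences and the Visit 6 versus Visit 4 comparison against zero, as planned. No change is needed in 11.5.5. The cost is one SAP line and a matching edit to one output table, with no new data.
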